12.3. Eligibility and Baseline Assessments

The following information will be collected at the baseline assessment:

- Data relating to the clinical assessment of eligibility
- Formal confirmation of eligibility

For participants that complete formal eligibility to proceed to registration the following baseline data will be recorded prior to registration:

- Demographic information
- Relevant medical history and clinical assessments
 - o BMI,
 - \circ index of multiple deprivation,
 - o ethnicity,
 - o mental health diagnoses,
 - smoking status and history,
 - symptom(s) prompting imaging and duration,
 - \circ Other parameters needed for lung cancer risk scores (PLCO_{M2012}/LLP_{v2}),
 - Name of General Practitioner who referred patient for chest X-ray and name of practice
- Questionnaire
 - health-related quality of life (EQ-5D-5L) in person/on paper/telephone/electronic administration (where applicable).

12.4. WP1 Registration

Registration will be completed at the baseline visit prior to booking the imaging appointments by a member of the research team after consent using the CTRU 24 hour system.

Following registration, the LDCT and CXR appointments will be arranged. Note: the LDCT must be completed before the CXR and within 10 working days of the GP CXR request, and there will be a maximum of 5 working days between the imaging tests.

The following information will be recorded **after** registration:

- Participant ID number
- Date of LDCT appointment
- Date of CXR appointment

12.5. LDCT and CXR appointments

Within 2 working days of the date of the participant's scheduled imaging appointment (s), the following information will be recorded:

- Whether the participant has attended the schedule appointment
- Related Unexpected Serious Adverse Events

If non-attendance at 1 or both of the imaging appointments, processes followed as per section 11.5.

12.6. HLH LDCT and CXR image upload

Within 2 working days of the image acquisition the following information will be recorded:

- Confirmation imaging was completed successfully

- Confirmation that letter has been sent for participants who don't attend either imaging appointment (where applicable)
- Confirmation of upload of images to Heart and Lung Health

Members of staff at recruiting centres, who are detailed on the authorised personnel log as responsible for this activity, will be provided with access to forward cases to the third-party system, and will be responsible for ensuring CXR and LDCT images are forwarded within 2 working days of image acquisition. Where available, old imaging will be transferred to HLH alongside the LDCT and CXR images acquired as part of MEDLEY. If available, the previous 3 thoracic CT scans and the previous 5 CXRs should be uploaded (of which 1 CXR should be over 1 year old).

12.7. HLH LDCT and CXR report transfer

Once reported by the HLH radiologists, reports will be returned to the relevant hospital PACS system. Depending on the local site arrangement, these results may automatically return to the hospital Radiology Information System (RIS), or need manually transferring by the study team from the hospital PACS into RIS within 2 working days of the report being available. The following information will be recorded:

- Duration between study upload to HLH and availability of completed report on HLH system
- Confirmation reports have been added to participant notes
- Radiological categorisation

12.8. Clinical Review/Action Meeting

The MEDLEY team at each centre will ensure the imaging results are received, reviewed and actioned in a timely manner (see Section 11.3 for further details). The study team will action any results reported by HLH according to local practice, which may include but not be limited to following up on findings or booking further tests and treatments. The clinical review of reports is strongly advised to take place within 5 working days of the reports being available and no more than 10 working days after the reports are available. A letter must be sent to the participant's GP using the standard template provided (see section 11.3). In addition, the following information will be recorded in the Clinical Review/Action Meeting eCRF:

- Clinical categorisation of LDCT report or CXR report if LDCT not completed
- Requirement for further review and outcome
- Actions (investigations/treatments)
- Confirmation that GP letter is sent

12.9. WP1&2 Follow Up Assessments

All participants will be followed up for a maximum of 52 weeks.

Month 4 Record Review and Questionnaire

A member of the research team will review the participant's medical records and record the following (relating to clinical activity resulting from MEDLEY imaging findings):

- Investigations
- Diagnoses (lung cancer (including stage), indeterminate nodules, and incidental findings) and date
- Treatments
- Possible harms

Participants will also complete an EQ-5D-5L via their preferred method of administration.

Month 12 Record Review

A member of the research team will review the participant's medical records and record the following:

- Investigations
- Diagnoses (lung cancer (including stage), indeterminate nodules and incidental) and date
- Treatments
- Possible harms

12.10. Site level imaging data

As the ability of the radiology services to meet demand for LDCT depends on a number of complex factors, in one or more sites we will collate some additional data which may include staffing levels, number of operational x-ray and CT machines, planned elective capacity, but also the non-attendance and cancellation rates, equipment unavailability due to breakdown and maintenance, cancelled lists for other reasons (e.g. staffing), as well competing priorities as any emergency or surveillance CT activity that takes place on elective CT lists. We will collate this for at least two non-consecutive months.

We will capture data from selected participating site(s) on site-level imaging capacity according to established methodology[32-36]:

- Total number of CT examinations (chest and other) undertaken per week
- Total number of CXR examinations (GP requested and total) undertaken per week
- Number of full-time equivalent radiographers and radiologists on rota per week.
- Proportion of CXR requests received that fulfil NG12 criteria on one day per week (week 1 = Monday, week 2 = Tuesday etc.)

12.11. WP1&2 Questionnaires

Consenting participants will complete an EQ-5D-5L questionnaire (See section 16.1.1) at baseline and 4 months via their preferred method. Non-responders will receive 1 reminder.

12.12. WP1 Protocol Deviations

The CTRU undertake to adopt all reasonable measures to record data in accordance with the protocol. Under practical working conditions, however, some minor variations may occur due to circumstances beyond the control the CTRU. All such deviations will be documented on the study records, together with the reason for their occurrence; where appropriate, deviations will be detailed in the published report.

12.13. Definition of End of Study

The end of the study is defined as the date of last data item for the last participant remaining in the study.

12.14. WP3 Qualitative Data collection

WP3 data collection will be completed by the qualitative research team at QMUL.

Data on participants' and patients' experiences and views on recruitment methods, the acceptability of the interventions, and their perceptions of trade-offs between LDCT and CXR, such as accuracy versus radiation exposure and logistical concerns will be collected through semi-structured

interviews. Interviews will be recorded and transcribed verbatim by a QMUL approved transcription service.

GP data collection will use both semi-structured questions and vignettes. These interviews will explore GP perspectives on the implementation of LDCT, risk-based patient selection, and the impact on their workload. GPs will be asked to state their preferences for different scenarios depicted in the vignettes, and to explore these in detail.

Using the World Café methodology, the stakeholder event will facilitate discussions across multidisciplinary panels, capturing qualitative insights on LDCT's acceptability and the feasibility of scaling up for a definitive trial.

13.0 WP1 Safety Monitoring/SAEs

13.1. General Definitions

A Serious Adverse Event (SAE) – means an untoward occurrence that:

- results in death,
- is life-threatening,
- requires hospitalisation or prolongation of existing hospitalisation,
- results in persistent or significant disability,
- consists of a congenital anomaly or birth defect,
- is otherwise considered medically significant by the Investigator.

A Related Unexpected Serious Adverse Event (RUSAE) means an SAE occurring to a research participant that in the opinion of the Chief Investigator was:

- 'Related' that is, it resulted from the administration of any of the research procedures, and
- 'Unexpected' that is, the type of event is not listed in the protocol as an expected occurrence.

Medical and scientific judgement must be exercised in deciding whether an event is serious (see protocol section 12.4 for Responsibilities). These characteristics / consequences must be considered at the time of the event and do not refer to an event which hypothetically may have caused one of the above.

13.2. Operational Definitions for (S)AEs

13.2.1. Expected AEs/SAEs – Not reportable

LDCT and CXR are low-risk with well-known safety profiles and as such, adverse events will only be reported if they meet the seriousness criteria (12.1), are related to the intervention, and occur on the day the intervention is received. AEs and SAEs which are not related to the study intervention (e.g., as a result of further investigations or treatment later in the patient pathway) are NOT reportable.

13.2.2. Recording & Reporting related SAEs and RUSAEs

All SAEs and RUSAEs occurring on the day of imaging must be recorded on the SAE/RUSAE Form and sent to the CTRU within 24 hours of the research staff becoming aware of the event. Once all

resulting queries have been resolved, the CTRU will request the original form should also be posted to the CTRU and a copy to be retained on site.

For each SAEs /RUSAE the following information will be collected:

- full details in medical terms and case description
- event duration (start and end dates, if applicable)
- action taken
- outcome
- seriousness criteria
- causality (i.e. relatedness to study drug / investigation), in the opinion of the investigator
- whether the event would be considered expected or unexpected.

Any change of condition or other follow-up information should be sent to the CTRU as soon as it is available or at least within 24 hours of the information becoming available. Events will be followed up until the event has resolved or a final outcome has been reached.

All RUSAEs will be reviewed by the CI and will be subject to expedited reporting to the Sponsor (dependent on Sponsor processes) and the main REC by the CTRU on behalf of the CI within 15 days.

13.3. Responsibilities

Principal Investigator / Authorised individual:

- 1. Checking for SAEs when participants attend their imaging appointments.
- 2. Judgement in assigning:
 - Seriousness
 - Relatedness
 - Expectedness
- 3. To ensure all RUSAEs are recorded and reported to the CTRU within 24 hours of becoming aware and to provide further follow-up information as soon as available.
- 4. To report RUSAEs to local committees in line with local arrangements.

Chief Investigator (CI) / delegate or independent clinical reviewer:

- 1. Assign relatedness and expected nature of SAEs where it has not been possible to obtain local assessment.
- 2. Undertake RUSAE review.
- 3. Review all events assessed as Related / Unexpected in the opinion of the local investigator. In the event of disagreement between local assessment and the CI, local assessment may be upgraded or downgraded by the CI prior to reporting to the main REC.

CTRU:

- 1. Expedited reporting of Related / Unexpected SAEs to the main REC and Sponsor within required timelines.
- 2. Preparing periodic safety reports to the SOC as appropriate.
- 3. Notifying Investigators of Related / Unexpected SAEs which compromise participant safety.

Study Oversight Committee (SOC):

In accordance with the study Terms of Reference for the SOC, periodically reviewing safety data to determine patterns and trends of events, or to identify safety issues, which would not be apparent on an individual case basis.

14.0 Outcome Measures

Outcomes are grouped according to type and those marked with an asterisk (*) will inform the decision to proceed to, and/ or inform the design of a definitive trial.

14.1. WP1 Quantitative outcomes

Outcomes are grouped according to type.

14.1.1 Outcomes relating to feasibility and deliverability of a definitive trial

- (*) Recruitment rate: number of participants recruited per centre-month
- (*) Proportions of eligible patients who consent/do not consent to participate, including assessment of non-participant characteristics associated with possible inequalities in participation
- (*) Time from site approach to opening, from opening to recruiting first participant, and duration of site recruitment

14.1.2 Estimates of diagnostic accuracy

- To inform sample size calculation for a definitive trial:
 - (*) Sensitivity & specificity of CXR using contemporaneous LDCT as a reference standard
 - Comparative sensitivity and specificity of LDCT and CXR using lung cancer diagnoses within one year (given the shorter follow-up this being a feasibility study) as reference standard
 - Sensitivity of CXR reported by cancer stage using contemporaneous LDCT as a reference standard
 - (*) Correlation/discordance between LDCT and CXR test results: proportions of paired tests that agree/disagree on presence of lung cancer.

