8.1. WP1

WP1 aims to recruit 900 participants with symptoms that may suggest lung cancer who have been referred from primary care for CXR from at least five UK centres. Patients will be recruited from secondary care sites and will follow a standard care pathway. All patients will receive a LDCT as well as a CXR, and both LDCT and CXR will be reported by independent consultant radiologists. The LDCT will be used to guide clinical care by the secondary care team and the report will be sent to the referring GP. All participants will be followed up for a maximum of 52 weeks. Outcomes are defined in section 14 grouped as i) feasibility of deliverability; ii) qualitative acceptability; iii) estimates of diagnostic accuracy; iv) imaging logistics; v) clinical outcomes; vi) economic outcomes. Those outcome measures informing the decision criteria to progress to definitive trial are stated in sections 14.1 and 14.2. The reference standard will be cancer diagnosis within 12-months of clinical follow-

up, but cancer diagnoses resulting from the paired LDCT (i.e. MDT approved diagnosis within 3 months of LDCT) will also be reported as a contemporaneous reference standard.

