15.1.4 Diagnostic accuracy

Crosstabulations of the results of each test will be reported (positive/negative/indeterminate). Sensitivities and specificities will be calculated for each test using the numbers of lung cancer cases or non-cases respectively and reported together with appropriate 95% confidence intervals.

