15.2 Sample Size

Based on realistically recruiting 5 participants per site per week (i.e. 20 per site per month) and allowing staggered opening of sites, it is estimated that 900 participants can be recruited to MEDLEY within a 12-month recruitment timeframe. Recruiting a total of 900 patients will permit estimation of a per-centre-month recruitment rate for a full diagnostic accuracy trial and relevant trial sample size parameters with acceptable precision. For the recruitment rate, using generalised linear modelling theory, and working with the log-likelihood and Hessian for a one-parameter Poisson model, 900 participants gives a 2-sided 95% confidence interval for relative precision as (1/1.068 to 1.068) times the estimated rate. For example, with 20 participants per centre-month recruited, then a 95% confidence interval for the true recruitment rate would be (18.7 to 21.4) per centre-month. Based on 2021/22 -level data, between 250-579 CXRs per week per site are requested [25]. Our unpublished analysis indicates 31% of CXRs fulfil NG12 criteria, and experience with the Yorkshire Lung Screening Trial demonstrates 50% of eligible patients are recruited. Hence the average recruitment rate of five/week/centre is realistic.

Sensitivities of CXR and LDCT will be estimated. We anticipate that prevalence of lung cancer detected will be at least 1.7%. This is based on the proportion of those who were diagnosed with lung cancer within two years following investigation with CXR and with similar characteristics as participants who will be recruited to MEDLEY [40]. Although the follow up period for MEDLEY will be one year, rather than two years, the number of cancers detected will exceed that which would be identified on CXR alone and it is likely that a substantial proportion of cancers not detected on CXR would take longer than two years to be diagnosed [41].

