As a feasibility study, MEDLEY has not been designed for any pre-specified precision (which would be the design criteria for a definitive trial). With a prevalence estimated as 1.7%, an estimated sensitivity of 90% would have an 95% exact confidence interval covering values as low as 72% (estimated using the Clopper-Pearson exact method). Other metrics including specificity of CXR/LDCT, proportions of concordant/discordant imaging results, proportions completing imaging, and proportions completing questionnaires would all have 2-sided 95% confidence intervals +/- 3.3% (estimated using the normal approximation method) assuming that a minimum of 97% of participants are included in estimates of specificity, and assuming a worst-case estimate of 50% where estimated variance is maximised.

We have used simulation to predict how precisely we will estimate the proportion of CXR requests that fulfil NG12 criteria. Assuming that there will be at least 169 centre-weeks of recruitment and that for each of these, GP CXR requests will be assessed for NG12 and those eligible contacted until 5 potential recruits are identified, we expect to estimate the proportion of requests fulfilling NG12 with a 95% confidence interval width of 2.4%, with the interval width being below 3.0% with 90%

probability. The simulation incorporated uncertainty in the population proportion of CXR requests fulfilling NG12 criteria (Beta distribution with parameters 31 and 69) and the proportion of CXR requests which do fulfil NG12 criteria resulting in a potential recruit (Beta distribution with parameters 5 and 5).

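### The starred LDCT–CXR discordance is taken over all paired tests, about 98% of them non-cancers, so it cannot size a definitive paired comparison of sensitivity

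*Protocol*

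**What the plan says.** All of this is in the Protocol; the SAP is not available.

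- **Section 14.1.2** lists accuracy outcomes intended to feed the sample size of a definitive trial. One starred item is "Correlation/discordance between LDCT and CXR test results: proportions of paired tests that agree/disagree on presence of lung cancer". Under section 14.0 a star means that the outcome informs the decision to proceed or the design of that trial.
- **Section 15.2** groups "proportions of concordant/discordant imaging results, proportions completing imaging, and proportions completing questionnaires" with specificity and says these "would all have 2-sided 95% confidence intervals +/- 3.3% (estimated using the normal approximation method", "assuming a worst-case estimate of 50% where estimated variance is maximised" and "assuming that a minimum of 97% of participants are included in estimates of specificity".
- **Section 15.1.4** promises cross-tabulations of test results, then states: "Sensitivities and specificities will be calculated for each test using the numbers of lung cancer cases or non-cases respectively". It names no paired difference and no LDCT-by-CXR table by cancer status.
- **Section 14.1.2** also stars the sensitivity of CXR against contemporaneous LDCT. Section 8.1 defines that reference as MDT-approved cancers resulting from the paired LDCT within 3 months. Comparative sensitivity and specificity of both tests against 12-month diagnosis is listed without a star.
- **Size and prevalence:** "WP1 aims to recruit 900 participants with symptoms that may suggest lung cancer" (section 8.1) and "We anticipate that prevalence of lung cancer detected will be at least 1.7"% (section 15.2).

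**The concern.** Every participant is to have both tests, so a definitive trial on this design would compare sensitivities within the same cancers. The number of cancers it needs depends on two quantities: the difference in sensitivity, and the proportion of cancers on which the tests disagree. The starred discordance is a different quantity. Taken over all pairs, it is mostly a measure of how often the tests disagree in people without lung cancer, and so it follows the two specificities.

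Reporting each test's sensitivity separately does not close the gap. Two marginal sensitivities fix the difference between the discordant cells but not their sum, and the sum enters the sample-size formula.

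What is at stake is the design output that MEDLEY exists to deliver. The discordance figure carrying a ±3.3% interval is not the one the definitive trial needs. The one it needs will be far less precise, and its second cell is not planned as an estimate.

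**Working it through.** **1. Which denominator does the protocol use?** Half-width = 1.96 × √(0.5 × 0.5 / n).

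- n = 900: 3.27%
- n = 873 (97% of 900): 3.32%
- n = 15 (cancers only): 25.3%

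The stated ±3.3% therefore reproduces with 873 to 900 pairs. Discordance is taken over all participants.

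**2. How many of those pairs are cancers?** 0.017 × 900 = 15.3, which leaves 98.3% non-cancers.

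**3. What drives all-pairs discordance?** The protocol gives no specificities, so the values below are assumptions, with test errors taken as independent in non-cancers. Non-cancer discordance = spX(1 − spL) + spL(1 − spX). All-pairs discordance = 0.983 × non-cancer discordance + 0.017 × within-cancer discordance. Within-cancer discordance runs from 21% to 33% (step 4).

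| CXR / LDCT specificity | All-pairs discordance | Share from cancers |
|---|---|---|
| 99% / 98% | 3.3–3.5% | 11–16% |
| 97% / 95% | 7.9–8.1% | 4.5–6.9% |
| 95% / 90% | 14.1–14.3% | 2.5–3.9% |
| 90% / 80% | 25.9–26.1% | 1.4–2.1% |

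Non-cancers dominate in every row.

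**4. What do the marginal sensitivities leave open?** Section 6.3 cites 94% (LDCT) and 73% (CXR) from a screening study, so d = 0.21. Let c be the proportion of cancers that are CXR-positive/LDCT-negative. Within-cancer discordance is ψ = d + 2c, and c can run from 0 to 1 − 0.94 = 0.06.

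Cancers needed = (1.96√ψ + 1.2816√(ψ − d²))² / d². Two-sided alpha 0.05 and 90% power are assumptions; the protocol sets neither for the definitive trial.

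| c | ψ | Cancers | Participants at 1.7% |
|---|---|---|---|
| 0 (nested) | 0.21 | 46 | about 2,700 |
| 0.06 × 0.73 = 0.044 (independent) | 0.298 | 67 | about 3,900 |
| 0.06 (maximum) | 0.33 | 75 | about 4,400 |

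With 94% against 80% (the top of the range section 6.3 gives for CXR in symptomatic patients), ψ runs from 0.14 to 0.26. The need is then 71 to 136 cancers, or about 4,200 to 8,000 participants. The undetermined cell moves the trial size by a factor of 1.6 (75/46) to 1.9 (136/71).

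**5. What if the all-pairs figure were put into the same formula?** With d = 0.21, the 95%/90% row (14.3%) returns 30 cancers, about 1,760 participants, against the 46 to 75 required. The 97%/95% row returns 15 and the 90%/80% row 58. In the 99%/98% row the discordance is below d² = 0.044 and the formula has no solution. The answer follows the assumed specificities, which should not enter a comparison of sensitivity.

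**6. What do the other planned outcomes recover?** Let a, b and c now be counts of cancers positive on both tests, on LDCT only and on CXR only. CXR sensitivity against LDCT-detected cancers is a/(a + b), so one minus it gives the LDCT-positive/CXR-negative share. If the same n cancers and the same positivity rule held throughout, b = (1 − that sensitivity) × SensLDCT × n and c = b − (SensLDCT − SensCXR) × n. Check with a = 10, b = 4, c = 1, n = 15: b = (4/14) × (14/15) × 15 = 4, and c = 4 − (14 − 11) = 1. In the protocol the first input uses cancers arising from the LDCT within 3 months, and the other two use 12-month diagnoses. The recovery is therefore only approximate.

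**7. Precision of the right quantity.** Exact 95% intervals with 15 cancers: 3/15 discordant gives 4% to 48%; 5/15 gives 12% to 62%.

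**The case against.** The strongest reply has four parts.

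- **The main cell is already a starred outcome.** CXR sensitivity against LDCT-detected cancers captures cancers seen on LDCT and missed on CXR. Section 15.1.4 also promises cross-tabulations, and section 15.1.1 a STARD diagram. This stands. A reader might infer that within-cancer discordance is not estimated at all, and the documents do not support that: one direction is estimated and the paired data are collected. The opposite direction is the gap, because a reference built from diagnoses resulting from the LDCT does not capture cancers that LDCT missed.
- **Table layout and paired intervals belong in a SAP.** This is true of the interval method and the table shell. It does not reach the outcome definition in section 14.1.2 or the ±3.3% in section 15.2. Both are fixed in the protocol, and both point to the all-participant denominator.
- **Fifteen cancers cannot size a trial precisely anyway.** This stands too. Section 15.2 says the study is not designed for a set precision, and section 16.4.3 plans simulation over sample sizes. It is a reason to state the real uncertainty, not to offer a precise estimate of a different quantity.
- **Nobody proposes putting the all-pairs figure into a within-cancer formula.** The protocol indeed gives no formula. A reader might also infer that such a calculation must fail or must undersize the trial. Neither holds in general: step 5 of the working shows that it depends on the specificities. The firm point is that the figure does not carry the information needed.

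**Conclusion.** The concern holds as a mismatch between a stated outcome and its stated purpose. The all-participant denominator is established by the protocol's own ±3.3%, and the dominance of non-cancers by its own 1.7% prevalence. With 94% against 73%, the unspecified CXR-positive/LDCT-negative cell separates 46 from 75 cancers, or about 2,700 from 4,400 participants. Those counts assume two-sided alpha 0.05, 90% power, 1.7% prevalence, and screening-study sensitivities that may not carry over to symptomatic patients. The shares in step 3 rest on assumed specificities, but the conclusion does not change across the range shown.

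No data are lost and nothing in the protocol prevents the right analysis. It is worth changing because the outcome is starred and is meant to shape the definitive trial.

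**What to change.** - **Section 14.1.2:** define the starred discordance outcome as the LDCT-by-CXR table, reported separately in reference-positive and reference-negative participants on the 12-month standard. Give both discordant cells with exact confidence intervals. Keep overall agreement as a descriptive line only.
- **Section 15.1.4:** add the paired differences (LDCT minus CXR) in sensitivity and in specificity, with confidence intervals that use the pairing.
- **Section 15.2:** confine the ±3.3% to proportions over all participants. State that within-cancer discordance rests on about 15 cancers, with an example such as 5/15 (exact 95% CI 12% to 62%).

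The cost is protocol and SAP wording and one extra table. No additional data, imaging or follow-up is needed.
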